## OVERALL RATIONALE FOR THE AMENDMENT

The main reason for this amended protocol is to replace the first 3 patients treated during the Dose Escalation Part because of uncertainties in the doses that they received and to restart the study at dose level 1 using a 3+3 design, following resolution of the full clinical hold.

In addition, minor editorial corrections (especially for consistency and clarity) have been made.

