- IMP-related adverse reaction (unless caused by disease progression or an obviously unrelated cause) lasting more than 2 weeks with failure to recover to baseline or improve to Grade ≤1.

The occurrence of DLTs will inform the dose recommendation that will be used during the Expansion Part.

Response assessment will be performed according to the International Working Group (IWG) 2003 recommendations for AML, the revised 2000 criteria for HR-MDS and the 2016 National Comprehensive Cancer Network (NCCN) Guidelines for ALL.

If at the end of a cycle the patient exhibits clinical benefit by symptoms or response criteria and does not meet study treatment discontinuation criteria, the patient may continue therapy until an unacceptable AE, disease progression, patient's decision to stop the treatment, or any other reason.

To minimize the risk of severe CRS, an intra-patient dose escalation in Cycle 1 is proposed, as shown in Table 1. Lead-in doses include the first 2 doses in Dose Level (DL) 1 and DL2 (ie, Week 1 and Week 2 administered doses), the first 3 doses in DL3 to DL5, and the first 4 doses in DL6 to DL8. After the lead-in doses, each patient will receive a fixed dose until the end of treatment, unless the dose needs to be decreased for safety reasons. DL1 to DL8 will achieve a range of lead-in doses from

During Cycle 1 and Cycle 2, pharmacokinetic and pharmacodynamic data will be collected that will be used, together with acute safety monitoring, to inform the choice of subsequent dose levels for both the Dose Escalation Part and the Expansion Part.

Table 1

	Cycle 1 (doses in ng/kg)											
Dose Level	W	l 1	W2	W3	W4	W5	W6					
	D1	D4	D8	D15	D22	D29	D36					
DL1												
DL2												
DL3												
DL4												
DL5												
DL6												
DL7												
DL8												

D=Day, W=Week

For subsequent cycles, patients will maintain the maximum weekly dose that they achieved in Cycle 1, as shown in Table 2.

Table 2

Dose		Cycle ≥2 (doses in ng/kg)								
Level	Week 1 Week 2	Week 5	Week 6							
DL1										
DL2										
DL3										
DL4										
DL5										
DL6										
DL7										
DL8										

Property of the Sanofi Group - strictly confidential

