### 6.3 MAXIMUM ADMINISTERED DOSE / MAXIMUM TOLERATED DOSE

The dose escalation will end when the MAD is reached, which will be defined as the dose at which ≥33% of evaluable patients have experienced an IMP-related DLT during the DLT observation period in a cohort of 6 patients.

The MTD will be defined as the highest dose level at which no more than 1 patient of a maximum of 6 patients experienced an IMP-related DLT.

The patient population evaluable for MTD determination in the Dose Escalation Part will consist of all patients who receive at least 5 out of 6 weekly IV administrations of SAR440234 in DL1 and DL2, patients who receive at least 6 out of 7 IV administrations of SAR440234 in DL  $\geq$ 3, and patients who discontinue the IMP before completion of Cycle 1 because of a DLT.

A patient who discontinues the IMP before the end of the DLT observation period or does not receive the planned dose for any reason other than DLT, will be replaced by enrolling another patient. The first 3 patients treated during the Dose Escalation Part of TED15138 will be replaced. Another 3 patients will be enrolled in DL1 and the trial will proceed according to the 3+3 design.

The dose level below the MAD will be considered the preliminary MTD, providing DLTs are observed in fewer than 2 of 6 treated patients (or fewer than one-third if more than 6 patients) at that dose level. Intermediate dose levels may be evaluated according to Study Committee recommendations. The MTD is generally the highest dose level at which at most 1 patient of a dose level cohort experiences a DLT.

Although the dose escalation process is guided by the safety evaluation during the DLT observation period, cumulative or irreversible toxicities observed in subsequent administrations should also be considered for the dose escalation and dose selection decisions (ie, smaller increases in dose, expansion of a given dose level, or an intermediate dose level), upon agreement between the participant Investigators and the Sponsor.

In the absence of an MTD, pharmacokinetic and pharmacodynamic parameters may help to define the recommended dose of SAR440234 to be tested in the expansion cohort part of the study.

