# 13.3.2 Patients evaluable for DLT assessment

The DLT-evaluable population in the Dose Escalation Part will include all patients who have received at least 5 out of 6 weekly IV administration of SAR440234 in DL1 and DL2, patients who have received at least 6 out of 7 IV administrations of SAR440234 in DL  $\geq$ 3, and patients who discontinue the IMP before completion of Cycle 1 because of a DLT.

A complete safety evaluation should be performed during the DLT observation period, and a DLT form should be completed at the end of the cycle. This concerns both patients followed up to the end of the evaluation period and patients who experienced a DLT validated by the Study Committee. Patients with incomplete safety evaluation during the DLT observation period and who experience a DLT during this period will be considered as evaluable for DLT.

The first 3 patients treated will be excluded from the DLT-evaluable population.

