# 13.3.3 Pharmacokinetic population

The pharmacokinetic population will include patients from the all-treated/safety population with at least 1 evaluable drug concentration after IMP administration (whatever the cycle and even if dosing is incomplete).

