3 ANALYSIS POPULATIONS

The following populations for analyses are defined:

Table 3 - Populations for analyses

Population	Description
Screened	All participants who have given their informed consent.
All-treated	All participants from the screened population and exposed to the investigational drug, regardless of the amount of treatment administered.
Efficacy	All participants from the all-treated population with at least one post-baseline evaluable disease assessment allowing status evaluation.
DLT-evaluable	All participants in the dose escalation part, who have received at least 5 out of 6, weekly IV administrations of SAR440234 in DL1 and DL2, or at least 6 out of 7 IV administrations of SAR440234 in DL \geq 3. Patients who discontinue the IMP before completion of Cycle 1 because of a DLT will also be included in the DLT-evaluable population. Patient who discontinues the study treatment before the end of Cycle 1 for another reason than DLT will be replaced.
Pharmacokinetic (PK)	All participants from the all-treated population with at least one drug concentration post-baseline (whatever the cycle and even if dosing is incomplete).
ADA	All participants from the all-treated population with at least 1 available ADA result (positive, negative or inconclusive) post-baseline.
Biomarker	All participants from exposed population with at least one valid assessment for: 
• CRP or ferritin, or• Cytokines, or• Disease molecular subtype, or• immunophenotyping by flow cytometry, or• MRD.

For any participant enrolled and treated more than once, only the data associated with the first enrollment will be used in any analysis population. The safety experience associated with any later enrollment will be reported separately.

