4.7.1.2 SAR440234 exposure

The dose information will be assessed by the following:

- Cumulative dose for SAR440234 (ng/kg): the cumulative dose is the sum of all doses from cycle 1 day 1 up to treatment discontinuation
- Actual dose intensity (ng/kg/week) for SAR440234:
$$\text{ADI} = \text{Cumulative dose (ng/kg)} / \text{Overall duration of exposure in weeks}$$
- Planned dose intensity (ng/kg/week) for SAR440234:

$$\text{PDI} = \text{Total planned dose (ng/kg)} / \text{Overall duration of exposure in weeks}$$

The total planned dose for SAR440234 will be calculated by the sum of the theoretical planned dose (ie, the intended dose as per CRF) over the duration of treatment.

- The relative dose intensity (RDI, in %) for SAR440234 is defined as

$$\text{Relative Dose Intensity} = \left(\frac{\text{Actual Dose Intensity}}{\text{Planned Dose Intensity}} \right) \times 100$$

It is an indicator of the feasibility of the chosen schedule of administration.

A listing will be provided for cumulative dose, actual dose intensity and relative dose intensity.

Dose or cycle modifications

- Cycle delay: A cycle is deemed to have been delayed if start date of the current cycle – start date of previous cycle >42 days.
- Dose delay: A dose is deemed to have been delayed if the infusion is made >1 day later than the scheduled administration.
- Dose omission: A dose is considered to be omitted if the dose is not administered at the scheduled visit and 1 or more doses are given afterwards.
- Dose interruption: An infusion is considered to be interrupted if the administration is stopped before the infusion is completed, regardless of whether or not the infusion is restarted.
- Dose reduction: a dose is deemed to have been reduced if the dose taken by a patient is lower than 80% of the intended dose.
- Reason for dose reduction.

Dose information variables will be provided in a listing:

- Cycle/day of occurrence
- Dose reduction Y/N
- Dose omission Y/N
- Dose interruption Y/N
- Cycle delay Y/N

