4.8.3 Biomarker analyses

Plasma levels of pro-inflammatory cytokines, including interleukin-6 and interferon- γ , as well as blood levels of 2 acute phase proteins, C-reactive protein (CRP) and ferritin, will be assessed during the trial.

Several immune populations and sub-populations will be assessed through immunophenotyping performed on blood and bone marrow samples. Different panels will be investigated such as the blasts, the plasmacytoid dendritic cells and basophils, the T cells, and the NK cells, granzyme B and interferon- γ , as well as analysis of T cell functional status including frequency of Tregs (CD4+CD25+CD127-) and expression of activation markers such as PD-1 and CD25.

All biomarkers will be summarized by dose level at baseline and over time by using descriptive statistics. For cytokines, the number of values below the LLOQ will be provided and for the computation of summary statistics, LLOQ/2 will be used to impute the test results with below LLOQ (BLOQ, ie, value<LLOQ).

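### The first 3 patients, whose true doses are uncertain, are removed only from the protocol's DLT set; the SAP omits even that, and by-dose-level PK and biomarker summaries still include them

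*Protocol*

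**What the plan says.** The overall rationale for Amendment 03 says the first 3 patients are replaced "because of uncertainties in the doses that they received". The summary-of-changes table adds that their PK profiles were abnormal and that they may at times have been overdosed. It also says their data belong in the safety database and not in the escalation decision.

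In the protocol's analysis-population section the only consequence is in 13.3.2: "The first 3 patients treated will be excluded from the DLT-evaluable population". The next section, 13.3.3, defines the PK population as treated patients "with at least 1 evaluable drug concentration after IMP administration", with no exception. The ADA population in 13.3.5 has none either. Section 13.4.5 assesses dose proportionality and accumulation in that PK population.

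SAP Table 3 defines the PK population as "All participants from the all-treated population with at least one drug concentration post-baseline" and the biomarker population as exposed participants with at least one valid assessment. Its DLT-evaluable definition counts infusions received, or discontinuation because of a DLT, and does not mention the first 3 patients. SAP Section 4.1 groups analyses by dose level where applicable, and Section 4.8.3 says: "All biomarkers will be summarized by dose level at baseline and over time".

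**The concern.** A dose-proportionality assessment, or any summary by dose level, needs a known dose for each patient. These 3 patients were replaced because that is missing, and it was their PK data that exposed the problem. Even so, the rules as written leave them in the PK and biomarker sets, and no rule says which dose level they are shown under.

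If they appear under the level they were assigned, any overdose raises apparent exposure and cytokine release at that level and flattens the dose-exposure relation. Adverse events and laboratory abnormalities after a possible overdose would be read as events of the assigned level.

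The SAP omission is a separate fault. Any of the 3 who meets its infusion count, or stopped because of a DLT, would count as DLT-evaluable under the SAP but not under the protocol. SAP Appendix 2 nevertheless records no changes to the protocol-planned analyses.

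**Working it through.** The plan gives no figure to reproduce. The check has two parts: the rules set side by side, and an illustration of size.

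**Where the first 3 patients stand under each rule**

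| Set or output | Protocol | SAP |
|---|---|---|
| DLT-evaluable | Excluded (13.3.2) | No exclusion (Table 3) |
| PK population | No exclusion (13.3.3) | No exclusion (Table 3) |
| Biomarker population | Not defined in 13.3 | No exclusion (Table 3) |
| Dose proportionality, accumulation | PK population (13.4.5) | Not listed in 4.8.1 |
| PK and biomarker summaries | By dose level (13.4) | By dose level (4.1, 4.8.3) |
| TEAE and laboratory tables | AE percentages within each dose level (13.4.4.2) | All-treated, by dose level (4.1, 4.7) |

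The protocol specifies the intended dose level only for patient disposition (13.2.1). Elsewhere both documents say dose level without defining it, and neither reassigns these patients to a verified dose.

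**Illustration of size**

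Inputs:
- 3 replacement patients at DL1 (Protocol 6.3, 11.2, 13.1.1).
- Overdose factor k: not given, so assumed. The low end, 1.3, is the 30% excess that the protocol uses to define an infusion overdose (10.5.5). The values 2 and 5 are arbitrary.
- Dose levels of the first 3: not given. Case A puts all 3 at DL1, so m = 3 of n = 6. Case B puts one of them in a level with 3 others, so m = 1 of n = 4.
- Exposure proportional to dose, and every sampled infusion of the affected patients overdosed k-fold.

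Ratio of the mean under the assigned level to the true mean:
- geometric: k^(m/n)
- arithmetic: (m·k + n − m)/n

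| k | A, geometric | A, arithmetic | B, geometric | B, arithmetic |
|---|---|---|---|---|
| 1.3 | 1.14 | 1.15 | 1.07 | 1.08 |
| 2 | 1.41 | 1.50 | 1.19 | 1.25 |
| 5 | 2.24 | 3.00 | 1.50 | 2.00 |

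For example, in case A at k = 2, √2 = 1.41 and (3·2 + 3)/6 = 1.50.

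**Effect on a dose-proportionality slope (case A, true slope 1.00)**

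Assume 3 patients per level plus the first 3 at DL1, with the dose doubling between levels. The doubling is an assumption because the dose tables are blacked out. With x as the level number counted from 0, least squares on the log scale gives a slope of 1 − 3·x̄·(ln k/ln 2)/Sxx.
- 3 levels explored: x̄ = 9/12 = 0.75 and Sxx = 8.25. The slope is 1 − 0.273·(ln k/ln 2), which is 0.73 at k = 2 and 0.37 at k = 5.
- 8 levels explored: x̄ = 84/27 = 3.11 and Sxx = 158.7. The slope is 0.94 at k = 2 and 0.86 at k = 5.

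The fewer levels explored, the larger the distortion. Leaving the 3 patients out returns every ratio and slope to 1.00 under the same assumptions.

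**The case against.** **Escalation.** A reader might infer that the doubtful data re-enter the escalation decisions, because the Clinical Trial Summary uses PK and PD data "to inform the choice of subsequent dose levels for both the Dose Escalation Part and the Expansion Part" and Section 6.3 says that, without an MTD, "pharmacokinetic and pharmacodynamic parameters may help to define the recommended dose". The documents do not support that. The summary-of-changes table says these patients' data are not used for the escalation decision. Escalation follows DLT counts (Section 6.2.2), and the protocol's DLT-evaluable set excludes them. What remains is narrower: the limit stands only in the rationale column of an amendment table, is not in the body text or the SAP, and says nothing about the RP2D.

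**Exposure.** A reader might also infer that the SAP misstates these patients' exposure because it uses "the intended dose as per CRF". It does not. That phrase defines the planned dose, which is the usual denominator for relative dose intensity. Cumulative and actual dose intensity use the doses recorded. Those records may be wrong for these 3 patients, but this rule is not the cause.

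**Listings.** Much of the SAP output is by patient: exposure, dose modifications, deaths, DLTs, AESIs, CRS and ADA. Protocol 13.4.5 also presents individual PK profiles. This stands, and it confines the point to the PK and biomarker summaries and the TEAE and laboratory tables.

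**Evaluable concentrations.** The protocol's PK definition requires an evaluable concentration, which could be used to set these patients aside. But the term is not defined, and the SAP drops it.

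**Early termination.** The SAP drops the efficacy and interim analyses, so harm through the RP2D is largely moot. That stands. The outputs that remain are safety, PK, immunogenicity and biomarkers, and this point concerns most of those.

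**Safety population.** Keeping the 3 patients in it is intended and is not a fault.

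**SAP version.** The SAP cites Amended Protocol 03 dated 11 July 2019, and the protocol in hand is dated 29 August 2019. That may or may not explain the missing exclusion. Either way, the two definitions now differ.

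**Conclusion.** The point holds as one about analysis sets and reporting. Patients whose true dose is unknown stay in the PK and biomarker populations and in summaries by dose level, with no rule for the dose they are shown under, and the SAP lacks the DLT exclusion that the protocol states. That they would appear under their assigned level is the likely reading, not stated text.

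The size is open. At the protocol's own 30% overdose threshold the effect on mean exposure at DL1 is modest, about 1.14- to 1.15-fold. At an assumed 2-fold or 5-fold overdose it would dominate that level's summary and could make a proportional drug look clearly less than proportional if few levels were explored. These figures assume that all 3 patients were at DL1, that every sampled infusion was affected, and that exposure is proportional to dose. The amendment speaks only of possible overdose at times, so the true effect may be smaller. It is worth correcting before reporting. The documents do not show that any escalation decision was compromised.

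**What to change.** 1. In Protocol 13.3.3 and 13.4.5 to 13.4.7, and SAP Table 3, 4.8.1 and 4.8.3, exclude the first 3 patients from by-dose-level PK, dose-proportionality, accumulation and biomarker summaries, and list their data individually.
2. Add their exclusion to the DLT-evaluable definition in SAP Table 3.
3. Keep them in the overall safety population. In by-level TEAE and laboratory tables, show them separately from the dose-level columns or mark them with a footnote; either would do.
4. State in the protocol body and the SAP that their data are not used for escalation, and extend that limit to the RP2D.

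The cost is wording and a listing, plus a footnote or one table column. No patients or procedures are added, and sample size, alpha and power do not change, because the protocol already replaces these patients. The downside is that by-level summaries lose 3 patients whose dose is uncertain.

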# 13.3.4 Activity/efficacy population

The activity/efficacy population will be defined as all patients with at least 1 post-Baseline evaluable disease assessment allowing status evaluation.

# 13.3.5 Anti-drug antibody population

The ADA population will include all patients from the all-treated/safety population with at least 1 available ADA result after IMP administration.

#### 13.4 STATISTICAL METHODS

Unless otherwise specified, analyses will be descriptive and performed based on the all-treated/safety population.

Continuous data will be summarized using number of available data, mean, standard deviation (StD), median, minimum, and maximum for each dose level. Categorical and ordinal data will be summarized using number and percentage of patients in each dose level.

### 13.4.1 Demographics and baseline characteristics

Standard demographic and baseline characteristics (including age, race, gender, ECOG performance status), medical history, cancer diagnosis will be collected at baseline and described by dose level. Genetic and molecular profiles of disease, if available, will be collected before study treatment.

Parameters will be summarized by dose level and overall using descriptive statistics.

# 13.4.2 Extent of investigational medicinal product exposure

The extent of IMP exposure will be assessed and summarized by dose level within the all-treated/safety population.

Duration of IMP exposure is defined as: last dose date – first dose date + 28 days, regardless of unplanned intermittent discontinuations.

In addition, in the Expansion Part of the study, dose information will be assessed for the following variables:

- The number of infusions.
- The cumulative dose at Cycle k is the sum of all doses from Cycle 1 to and including Cycle k, where k is based on Investigator's report.
- Actual dose intensity (ADI), defined as the cumulative dose divided by the number of weeks on study treatment.
- Relative dose intensity (RDI), defined as the ratio of the actual dose intensity to the planned dose intensity. The relative dose intensity is an indicator of the feasibility of the chosen schedule of administration.
- Cycle delay: A cycle is deemed to have been delayed if start date of the current cycle start date of previous cycle >42 days.
- Dose delay: A dose is deemed to have been delayed if the infusion is made >1 day later than the scheduled administration.
- Dose omission: A dose is considered to be omitted if the dose is not administered at the scheduled visit and 1 or more doses are given afterwards.
- Dose interruption: An infusion is considered to be interrupted if the administration is stopped before the infusion is completed, regardless of whether or not the infusion is restarted.
- Dose reduction and reason for dose reduction.

Dose information variables will be summarized descriptively (n, mean, standard deviation, median, Q1:Q3, minimum, and maximum). Analyses will be performed based on the number of patients and on the number of cycles.

# 13.4.3 Prior/concomitant medication/therapy

Medications will be summarized by treatment group according to the WHO-DD dictionary, considering the first digit of the ATC class (anatomic category) and the first 3 digits of the ATC class (therapeutic category). All ATC codes corresponding to a medication will be summarized. Patients will be counted once in each ATC category (anatomic or therapeutic) linked to the medication.

Medications of specific interest such as antibiotics and hematopoietic growth factors (G-CSF, GM-CSF and erythropoietin or red blood cells transfusion) will be summarized and listed by dose level.

Further treatment of interest for the analysis and given to the patient after withdrawal from IMP will be listed.

